#### **8.4 Supply of Study Drug at the Site**

The Sponsor (or designee) will supply Study Drug to the investigational sites through hospital pharmacy.

#### **Dosage/Dosage Regimen**

- fluvastatin 20 mg by mouth as a 20 mg Lescol® capsule
- 30-min intravenous infusion of rifampin (Rifadin®, Sanofi-Aventis, Bridgewater, NJ) 600 mg in 10 ml sterile normal saline
- rifampin 600 mg oral by mouth as two 300mg rifadin capsules for 5 days in the morning

#### **Dispensing**

The investigator has authority to dispense the drug

#### **8.41 Administration Instructions**

Patient will take two 300 mg rifampin capsules by mouth for the 5 days prior to the study period 1 and another two 300 mg rifampin capsules during fluvastatin washout day (between study periods 1 and 2). During study periods 1 and 2, subjects will take fluvastatin 20 mg by mouth as a 20mg lescol capsule. Subjects will also receive 30-min intravenous infusion of rifampin (Rifadin®, Sanofi-Aventis, Bridgewater, NJ) 600 mg in 10 ml sterile normal saline at a rate of 20 mg/min, administered immediately prior to oral fluvastatin dosing on one of the study periods. All subjects will be asked to abstain from caffeinated beverages, alcoholic beverages, all fruit juices, oranges, and grapefruits from 7am the day before each study period until the study is complete

#### **8.5 Supply of Study Drug at the Site**

The investigator will supply study drug to the investigational sites.

#### **Storage**

Study drugs should be stored by the study site at controlled room temperature, 15 to 30°C (59 to 86°F). If the temperature of study drug storage in the clinic/pharmacy exceeds or falls below this range, this should be reported to the Sponsor or designee and captured as a deviation. It is important store the medication in original packaging (foil pouch and protected from light) at room temperature.

#### **8.5 Study Drug Accountability**

An accurate and current accounting of the dispensing and return of study drug for each subject will be maintained on an ongoing basis by a member of the study site

staff. The number of study drugs dispensed and returned by the subject will be recorded on the Investigational Drug Accountability Record. The study monitor will verify these documents throughout the course of the study.

### **8.6 Measures of Treatment Compliance**

Subject's daily rifampin dose will be verified by online video chat every morning during the 5 days prior to study, and on the one day washout period.

During study periods 1 and 2, the investigator will monitor the subjects when they take fluvastatin and when they undergo the 30-min intravenous infusion of rifampin (Rifadin®, Sanofi-Aventis, Bridgewater, NJ) 600 mg in 10 ml sterile normal saline at a rate of 20 mg/min.

## **9. STUDY PROCEDURES AND GUIDELINES**

A Schedule of Events representing the required testing procedures to be performed for the duration of the study is diagrammed in Appendix 1.

Prior to conducting any study-related activities, written informed consent and the Health Insurance Portability and Accountability Act (HIPAA) authorization must be signed and dated by the subject. If appropriate, consent must also be obtained prior to conducting any study-related activities.

### **9.1 Clinical Assessments:**

#### **Concomitant Medications**

Only subjects who take no other medications two weeks prior to the study and during the time course of the study including prescription medications, over-the-counter medications, dietary supplements, or drugs of abuse will be allowed to participate in the trial.

#### **Demographics**

A descriptive analysis of the demographic characteristics of the study subjects will be performed. Demographic characteristics of interest are age, race, height, weight and gender will be recorded at screening.

#### **Medical History**

Relevant medical history, including history of current disease, other pertinent respiratory history, and information regarding underlying diseases will be recorded at screening

#### **Physical Examination**

A complete physical examination will be performed by either the investigator who is a physician at screening visit. Qualified staff (MD) may complete the

abbreviated physical exam at all other visits. New abnormal physical exam findings must be documented and will be followed by a physician or other qualified staff at the next scheduled visit.

### **Vital Signs**

Body temperature, blood pressure, pulse and respirations will be performed after resting for 5 minutes at the screening.

### **Adverse Events**

Information regarding occurrence of adverse events will be captured throughout the study. Duration (start and stop dates and times), severity/grade, outcome, treatment and relation to study drug will be recorded on the case report form (CRF).

## **9.2 Clinical Laboratory Measurements**

### **Hematology**

Blood will be obtained and sent to each site's clinical hematology lab for a complete blood count (hemoglobin, hematocrit, red blood cell count, white blood cell count, white blood cell differential, and platelet count), erythrocyte sedimentation rate (ESR), and serum C-reactive protein (CRP) determinations for assessment of systemic evidence for infection and/or inflammation.

### **Blood Chemistry Profile**

Blood will be obtained and sent to site's clinical chemistry lab for Hgb, HCT, RBC, Plt, WBC with differential, Ca++, Na+, K+, Cl-, CO2, glucose, serum creatinine, BUN, phosphorus, AST, ALT, alkaline phosphatase, CPK, total bilirubin, albumin, total protein, cholesterol, and triglycerides.

### **Pregnancy Test**

A urine or serum pregnancy test will be obtained from female subjects who are of childbearing age prior to their participation in the study.

### **Urinalysis**

Urine will be obtained and sent to each site's clinical laboratory for determination of (list as applicable) color, specific gravity, pH, protein, glucose, ketones, and blood.

## **9.3 Pharmacokinetic Measurements**

Blood for determination of serum concentrations of fluvastatin will be collected 0, 0.33, 0.67, 1, 1.5, 2, 2.5, 3, 4, 6, 9, and 12h after fluvastatin dosing. Plasma will be separated and stored at -80°C until analysis of drug levels.

Plasma concentrations of fluvastatin and rifampin in all collected plasma samples will be measured via a previously validated tandem liquid chromatography mass spectrometry (LC-MS/MS) method. Determined plasma concentrations of fluvastatin will then be modeled using pharmacokinetic modeling software to calculate the corresponding AUC, oral clearance, and oral volume of distribution of fluvastatin in the treatment groups.

#### **9.4 Research Laboratory Measurements**

Cell Count and Differential blood sample (30mL) for determination of Hgb, HCT, RBC, Plt, WBC with differential will be collected during the screening visit.

### **10 EVALUATIONS BY VISIT**

#### **10.1 Screening Visit (at least one week prior to study period 1)**

1. Written informed consent will be obtained.
2. A medical history and a physical exam including vital signs (oral temperature, heart rate, blood pressure, and respiratory rate), height, and weight will be performed. Subjects will also be asked about prescriptions, dietary supplements, and illegal drug use.
3. Blood (30 ml) and urine tests (Hgb, HCT, RBC, Plt, WBC with differential, Ca++, Na+, K+, Cl-, CO2, glucose, serum creatinine, BUN, phosphorus, AST, ALT, alkaline phosphatase, CPK, total bilirubin, albumin, total protein, cholesterol, triglycerides, urinalysis).
4. For female subjects, a urine pregnancy test will be obtained.

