## 4. STUDY DESIGN

### 4.1 Study Overview

The effect of rifampin on the pharmacokinetics of fluvastatin under a hepatic enzyme induced state will be studied in healthy volunteers in a two-period, randomized, unblinded, crossover clinical trial. For the first 5 days of the trial, the patients will be pretreated with 600mg oral rifampin (two 300mg rifadin capsule) once daily to induce hepatic enzymes (and transporters). For study period 1, subjects will be randomized to one of two treatment groups:

- (i) one oral dose of fluvastatin (Lescol®) 20mg capsule
- (ii) one oral dose of fluvastatin (Lescol®) 20mg capsule immediately following a 30-min intravenous infusion of rifampin 600mg in 10ml Normal Saline

The two study periods will ideally be on a Tuesday and Thursday, separated by one day of fluvastatin washout. The oral food intake will be standardized and subjects will be instructed to fast overnight the day before study period 1 and period 2, and for 3h post-dosing. In both treatments, venous blood samples (8ml each) will be drawn at 0, 0.33, 0.67, 1, 1.5, 2, 2.5, 3, 4, 6, 9, 12h after fluvastatin dosing. During the 1 day of fluvastatin washout, patients will continue pretreatment with one 600mg dose of oral rifampin. Period 2 will begin after 1 day of fluvastatin wash out, when subjects will receive the second treatment, followed by blood draws at the same time points after fluvastatin dosing. If study period two does not follow one day after study period one, it will most likely be conducted on Tuesday or

Thursday of the following week. In this case, the subjects would be maintained in a state of induction of hepatic enzymes by the same preinduction regimen with 600 mg of oral rifampin for 5 days before study period 2.

	Period 1	Period 2
Group 1	A	B
Group 2	B	A

A= fluvastatin; B =rifampin +fluvastatin

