## 6.2 Inclusion Criteria

1. Healthy male or female, ages 18-65 years old, with no current medical conditions or active diagnoses as determined by the study doctor based on history, physical exam, and laboratory evaluations.
2. Subjects who take no other medications two weeks prior to the study and during the time course of the study including prescription medications, over-the-counter medications, dietary supplements, or drugs of abuse.
3. Subjects able to maintain adequate birth control during the study independent of hormonal contraceptive use (use of condoms).
4. Subjects able to abstain from grapefruit, grapefruit juice, oranges, orange juice, caffeinated beverages and/or alcoholic beverages from 7am the day before the study to completion of that study day.
5. Participants determined to have normal liver and kidney function as measured at baseline (ALT:  $\leq 2x$  upper level of normal (ULN), AST:  $\leq 2x$  ULN, SCr:  $\leq 1.5x$  ULN, T. Bili: 0.1-1.2mg/dL, Albumin: 3.4 – 4.7 mg/dL).
6. BMI between 18.0 - 30 kg/m^2 o Subjects capable of fasting from food and beverages at least 8 hours prior to medication dosing.
7. Be able to read, speak, and understand English.
8. Subjects capable of providing informed consent and completing the requirements of the study.

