#### **10.2 Study period 1 (Tuesday of the Week):**

1. For female subjects, a urine pregnancy test will be performed.
2. For the purpose of administering rifampin and drawing blood samples, two indwelling peripheral venous catheters will be inserted aseptically into the forearm vein by a nurse in the CRC immediately prior to medication administration. The rifampin catheter will be removed immediately after rifampin administration, the second catheter will be removed after the final blood draw. If the catheter malfunctions and needs to be removed prior to the last blood draw, a subject may choose to have remaining blood draws via peripheral venous needle sticks or have a new catheter placed.
3. **Dose study medications**- Subjects will receive the pre-treatment dose two 300mg Rifampin Capsules as 300mg Rifadin® capsules for the 5 days prior to the study period 1. Subjects will receive one of the following dose of medications:
  - a. Dose fluvastatin 20 mg by mouth as a 20 mg Lescol® capsule
  - b. Dose rifampin 600mg IV infusion over 30 minutes (t = -30 minutes) followed by a dose fluvastatin 20 mg by mouth as a 20 mg Lescol® capsule (t = 0 minutes)

The order in which subjects receive the above treatments will be randomized via random number generator.

4. **Serial blood sampling-** Venous blood samples (8 mL) will be drawn at 0, 0.33, 0.67, 1, 1.5, 2, 2.5, 3, 4, 6, 9, and 12h after fluvastatin dosing. Plasma will be separated and stored at -80°C until analysis of drug levels.

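### Induced-state protocol: no maximum age is set for the pregnancy test that precedes the first oral rifampin dose, and the next test comes after five doses

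*Combined protocol and SAP*

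**What the plan says.** All references are to the induced-state protocol unless stated.

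- **Section 10.1** sets the screening time by a minimum only: "Screening Visit (at least one week prior to study period 1". Item 4 there reads "For female subjects, a urine pregnancy test will be obtained".
- **Section 9.2** has a general clause: "A urine or serum pregnancy test will be obtained from female subjects who are of childbearing age prior to their participation in the study". No day or window is given.
- **Section 4.1** places first exposure ahead of Period 1: "For the first 5 days of the trial, the patients will be pretreated with 600mg oral rifampin". **Section 8.41** agrees: "Patient will take two 300 mg rifampin capsules by mouth for the 5 days prior to the study period 1".
- **Section 10.2**, headed for the Period 1 day: "For female subjects, a urine pregnancy test will be performed". Section 10.3 has the same requirement for Period 2.
- **Section 4.1** also provides for a delayed Period 2, with induction maintained "by the same preinduction regimen with 600 mg of oral rifampin for 5 days before study period 2".
- **Section 6.2, item 2** admits "Subjects who take no other medications two weeks prior to the study and during the time course of the study". Section 6.3, item 2 excludes only people whose chronic medicine cannot be stopped.
- **Section 8.6** describes a video check of each morning's capsule during the lead-in. No visit or test is described for those days.
- **Appendix 1** marks the pregnancy test at screening only, although sections 10.2 and 10.3 require it in both periods.

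In the single-dose protocol, section 10.2 puts a urine pregnancy test on the day of first study drug.

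**The concern.** In the single-dose protocol the Period 1 test is a same-day check before any drug. The induced-state protocol keeps that test on the Period 1 day but moves first exposure five days forward, so the test now follows a full course of rifampin. What stands before that course is a screening test with a minimum interval and no maximum.

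The stake is subject safety, not inference. The volunteers receive no direct benefit (section 2.1) and pregnancy is an exclusion (section 6.3, item 9), so pregnancy status should be confirmed close to first exposure. A woman who conceives between screening and the first capsule, or whose pregnancy was too early to detect at screening, would take five doses before the next test. A positive result at Period 1 is then a listed reason for discontinuation (section 12.1), but the exposure has already occurred.

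**Working it through.** Take Period 1 as day 0.

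**The plan's own calendar.** Capsules on days -5 to -1, Period 1 on day 0, a capsule on washout day 1, Period 2 on day 2. Span = 2 - (-5) + 1 = 8 days, with 5 + 1 = 6 capsule days. Both match the Synopsis (about 8 days, capsules on 6 days), so the day count is sound.

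**Age of the screening test at capsule 1.** Age = (-5) - (screening day), with screening on day -7 or before.
- Minimum: (-5) - (-7) = 2 days.
- Maximum: none stated.
- Single-dose protocol, for comparison: test and first drug on the same day, 0 days.

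**Exposure before the next test.** 5 × 600 mg = 3,000 mg.

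**A case the eligibility rules produce.** Consent and the medication questions both take place at screening. Suppose a woman stops a stoppable medicine that day and must then be medication-free for two weeks before the study.
- Study starts at capsule 1 (the sense of section 4.1): screening on day -5 - 14 = -19 or before, so the test is at least 14 days old.
- Study starts at Period 1 (the sense of section 8.6): screening on day -14 or before, so the test is at least 14 - 5 = 9 days old.

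**Does other text set a maximum?**
- *Synopsis, about 8 days.* This is exactly capsule 1 to Period 2. Including screening on day -7 gives 2 - (-7) + 1 = 10 days, so the phrase does not bound screening.
- *Appendix 1 footnote, ±2 days.* No screening day is stated for it to modify. If day -7 is taken as nominal, the window is days -9 to -5. The one-week minimum cuts this to days -9 to -7, giving an age of 2 to 4 days. Ignoring that minimum, the age is 0 to 4 days.
- *Screening one week before the study.* This wording is in the single-dose Synopsis and is not repeated in the induced-state text.
- *Section 9.2.* A screening test of any age satisfies it.

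**Effect of a 7-day rule (7 is illustrative).** The earliest screening test needing no repeat is on day -5 - 7 = -12. Screening on days -12 to -7 (6 calendar days) gives a test 2 to 7 days old. Anything older is repeated on capsule day 1.

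**Delayed Period 2.** With Period 1 on a Tuesday and Period 2 on the next week's Tuesday or Thursday (day 7 or 9), re-induction starts on day 7 - 5 = 2 or 9 - 5 = 4. The Period 1 test is then 2 or 4 days old. It exceeds 7 days only if Period 2 falls after day 7 + 5 = 12.

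**The case against.** The best opposing case is that the safeguards exist and one number is missing. Tests are required at screening and in both periods, contraception is mandatory, and women who are pregnant or trying to conceive are excluded. The documents also suggest that screening was meant to be close to dosing. The Synopsis total of 27.5 hours exceeds two 13-hour stays plus six 5-minute doses (26 + 0.5 = 26.5), so it counts at least part of the screening visit within the stated 8 days or so. Appendix 1 marks dispensing and randomization at screening alongside the pregnancy test. On that reading the test is 2 to 4 days old. The 9- and 14-day figures need a particular subject, no frequency is given, and the documents contain neither a fetal-risk figure nor a test sensitivity.

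Much of this stands as a limit on importance. The case is uncommon, its benefit cannot be sized, and if screening falls near day -7 little is at stake. It does not supply the missing maximum. The hours argument is weak: the full sum is 26.5 + 2 = 28.5, not 27.5. The single-dose Synopsis likewise gives 27 hours against 26 for the stays, yet describes about 2 days, which leaves out its own screening visit a week before. Dispensing at screening fits capsules taken home with no later check before the first one. The footnote cannot turn a stated minimum into a maximum. The single-dose protocol's same-day test is a comparison, not a standard that this protocol breached.

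**Conclusion.** The concern holds, as a minor one. Followed as written, the induced-state protocol accepts a negative pregnancy test at least 2 days old, with no upper limit, before a five-day rifampin course, and repeats it only after 3,000 mg has been taken. For a woman who stops a medicine on the screening day, the test is at least 9 days old (study starting at Period 1) or 14 days old (study starting at capsule 1). On the reading most favourable to the plan the age is 2 to 4 days.

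This rests on capsules starting on day -5 and on section 10.1 being applied literally. A recent test lowers, but does not remove, the chance of exposing an early pregnancy. The AUC comparison, the type I error rate and power are unaffected, and the single-dose protocol does not have this gap.

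**What to change.** In sections 10.1 and 10.2 of the induced-state protocol, require a negative urine pregnancy test within a short stated time before the first oral rifampin capsule, for example 7 days. If the screening test is older than the limit, repeat it before capsule 1. A home urine test shown on the first morning's video call, already scheduled in section 8.6, would do. Limit the age of the test, not of the whole screening visit: a 7-day screening window would conflict with the two-week medication stop for women who stop at screening. Mark this test and the Period 1 and Period 2 tests in Appendix 1. A further test before re-induction is optional; under the same 7-day rule it is needed only if Period 2 is more than 12 days after Period 1.

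The cost is one sentence, the table marks, a short home-test instruction, and one urine kit for each woman whose screening test has passed the limit at capsule 1. There is no new clinic visit, no additional subject and no change to the analysis.

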#### **10.2 Study period 1 (Tuesday of the Week):**

1. For female subjects, a urine pregnancy test will be performed.
2. For the purpose of administering rifampin and drawing blood samples, two indwelling peripheral venous catheters will be inserted aseptically into the forearm vein by a nurse in the CRC immediately prior to medication administration. The rifampin catheter will be removed immediately after rifampin administration, the second catheter will be removed after the final blood draw. If the catheter malfunctions and needs to be removed prior to the last blood draw, a subject may choose to have remaining blood draws via peripheral venous needle sticks or have a new catheter placed.
3. **Dose study medications**- Subjects will receive the pre-treatment dose two 300mg Rifampin Capsules as 300mg Rifadin® capsules for the 5 days prior to the study period 1. Subjects will receive one of the following dose of medications:
  - a. Dose fluvastatin 20 mg by mouth as a 20 mg Lescol® capsule
  - b. Dose rifampin 600mg IV infusion over 30 minutes (t = -30 minutes) followed by a dose fluvastatin 20 mg by mouth as a 20 mg Lescol® capsule (t = 0 minutes)

The order in which subjects receive the above treatments will be randomized via random number generator.

4. **Serial blood sampling-** Venous blood samples (8 mL) will be drawn at 0, 0.33, 0.67, 1, 1.5, 2, 2.5, 3, 4, 6, 9, and 12h after fluvastatin dosing. Plasma will be separated and stored at -80°C until analysis of drug levels.

### 10.3 Visit 3 (Thursday of the week )

#### 1. Admit to Clinical Research Center (CRC) at UCSF -

During each study period, subjects will be admitted to the Clinical Research Center (CRC) at UCSF (12th Floor Moffitt Hospital). Subjects will be discharged after the 12 hour blood sample.

#### 2. Urine Pregnancy Test - For female subjects, a urine pregnancy test will be performed.

3. **Catheter placement-** For the purpose of administering rifampin and drawing blood samples, two indwelling peripheral venous catheter will be inserted aseptically into the forearm vein by a nurse in the CRC immediately prior to medication administration. The rifampin catheter will be removed immediately after rifampin administration, the second catheter will be removed after the final blood draw. If the catheter malfunctions and needs to be removed prior to the last blood draw, a subject may choose to have remaining blood draws via peripheral venous needle sticks or have a new catheter placed.

4. **Dose study medications-** Subjects will receive the pre-treatment dose two 300mg Rifampin Capsules as 300mg Rifadin® capsules during one day washout of fluvastatin. Subjects will receive one of the following dose of medications:

- a. Dose fluvastatin 20 mg by mouth as a 20 mg Lescol® capsule
- b. Dose rifampin 600mg IV infusion over 30 minutes (t = -30 minutes) followed by a dose fluvastatin 20 mg by mouth as a 20 mg Lescol® capsule (t = 0 minutes)

The order in which subjects receive the above treatments will be randomized via random number generators.

5. **Serial blood sampling-** Venous blood samples (8 mL) will be drawn at 0, 0.33, 0.67, 1, 1.5, 2, 2.5, 3, 4, 6, 9 and 12h after fluvastatin dosing. Plasma will be separated and stored at -80°C until analysis of drug levels.

6. **Safety Monitoring-** At study completion, subjects will have repeat physical examination and repeat hematology, chemistries, liver, renal and coagulation laboratories for safety monitoring.

